A total of 1ml (40 mg) will be injected intra-articularly after synovial fluid aspiration 'to dryness' either once (at study entry or 2 weeks after injury) or twice (at both study entry and 2 weeks after injury).

Rational for including pediatric population

The specific reason for enrolling the age group of children aged 14-17 is that these children have a musculoskeletal physiology like adults.

- Their major growth plates are closed.
- These patients may be treated surgically like adult patients with exactly the same surgical preparation, technique and rehabilitation as adults.
- Children, particularly girls, between the ages of 14 and 18 have the highest statistical risk in any population of tearing their Anterior Cruciate Ligament.²⁵
- Children in this age group are particularly vulnerable to the later development of osteoarthritis. Lohmander et al showed that young female soccer players in this age group developed symptomatic knee Osteoarthritis secondary to the ACL injury within 12 years of the injury.²⁴ One could therefore argue that particularly children between completed puberty and 18 years of age have to be the patients requiring most of our concern regarding development of OA.

By slowing the initial inflammatory process after injury and preventing the significant quadriceps muscle shutdown early, we aim to work towards this goal in this trial. We therefore conclude that given the limited risk of local side effects and the potential large benefit that this study would provide to the scientific community and its potential to significantly improve and alter patient care of young individuals suffering ACL injuries it is not reasonable to withhold pediatric patients aged 14-17 from this important trial.

RESEARCH OBJECTIVES OF THE CURRENT STUDY:

The research objectives of this study are:

1. Test the efficacy of Triamcinolone to alleviate knee pain (KOOS, IKDC) and improve patient-reported outcomes (PRO) following ACL rupture in a randomized, placebo controlled, double blinded, clinical trial. Triamcinolone will be administered intra-articularly within 1 week of ACL injury or at 2 weeks after ACL injury, or at both time points and compared with saline control injections. Patients will be evaluated at 5 post-injury time points (1-2 days, 12-14 days, 2 weeks post-op, 4 weeks post-op, 6 months

- post-op, and 24 months post-op) following ACL reconstruction.

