2. Determine if intra-articular Triamcinolone therapy improves levels of a panel of inflammatory (cytokine), meniscus and cartilage metabolism and oxidative stress biomarkers as measured in synovial fluid from patients at relatively short-term time points after ACL injury (1-7 days, 10-17 days after injury and at time of surgery). Biomarkers to be tested include IL-1 α , IL-1 β , Collagen type I (NtxI) and collagen type II (CTXII) breakdown products, cartilage oligomeric protein (COMP) and glycosaminoglycan (GAG) and Xanthine Oxidase. Additionally, the change in IL-1 α and IL-1 β levels in the Triamcinolone treated and placebo individuals will be evaluated specifically for association with pain and function outcomes.

RESEARCH OBJECTIVES OF EXTENDED FOLLOW-UP SUB-STUDY:

1. Determine if joint health as evaluated by MRI at 24 months following ACL injury is influenced by the initial treatment with Kenalog. Two years following ACL injury MRI analysis using standardized T2-mapping will be performed on 10 control subjects and 10 subjects who have received Kenalog injections.

INVESTIGATIONAL PLAN

Description of Overall Study Design and Plan (See Figure 1 for study timeline)

This study is a multicenter, randomized, placebo controlled, double blinded, clinical trial. This trial will enroll 68 subjects between the ages of 14 and 33. This trial will be conducted at two clinical centers, the University of Kentucky and Vanderbilt University, as well as established criteria and support of the Multicenter Orthopaedic Outcome Network (MOON). A sub-study involving extended follow-up of patients, 24 months post-surgery will occur at the University of Kentucky clinical center only. This sub-study will involve 20 subjects of the initial University of Kentucky cohort returning for one additional follow-up MRI.

Description of observations and measurements to be made in this study:

[figure not shown]

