Assessment of Pain and Function by KOOS – This trial will use the standardized patient self-report Knee Injury and Osteoarthritis Outcome Score (KOOS) instrument to assess pain and function in response to the intervention for acute ACL injury. The KOOS consists of 5 subscales (pain, other symptoms, function in daily living, function in sport and recreation, and knee-related quality of life). The 5 separate subscales provide a complete picture of subjects' perceptions of their knee injury and consequences to their daily activities, etc.. KOOS includes the WOMAC osteoarthritis index, which allows for potential comparison with other earlier studies. The KOOS has high test-retest reproducibility (ICC > 0.75). The KOOS subscales for function in sport and recreation and knee-related quality of life have been shown to be the most sensitive subscales pre-operatively and change the most post-operatively (44). This trial will supplement the KOOS with function score assessments from the International Knee Documentation Committee (IKDC) form for evaluation of knee ligament injuries [45]. In addition to the KOOS and IKDC, current physical activity level at the 24 month follow-up study will be evaluated using the MARX activity scale.

Specific Pain assessments - Pain coping strategies are important in understanding improvements in pain and psychological disability [46-48]. This trial will use a simple Likert pain scale, the Coping Strategies Questionnaire (CSQ) and 'pain catastrophizing' as pain assessment tools

(Figure 2). Pain catastrophizing has been identified as one of the strongest predictors of pain and has been defined as "an individual's tendency to focus on and exaggerate the threat value of painful stimuli and negatively evaluate one's own ability to deal with pain." Not only do individuals who catastrophize, experience more experimental pain [49-52] but also, catastrophizing has been shown to account for 7% to 31% of the variance in pain ratings in varied populations of patients having persistent pain. It has been associated with heightened anxiety, depression, increased pain behaviors, increased use of health care services and analgesic medication and thus,

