The power calculations include several caveats. The power calculation was performed based upon the use of a IL-1 receptor antagonist. There is no clinical data available in a young patient population with knee ligament injuries regarding their pain improvement after cortisone injection. The IL1RA data is the most comparable. Cortisone is a wider spectrum anti-inflammatory than IL-1RA and thus may have a larger effect on pain control that may be longer lasting. In that case our study may be over-powered. First, for purposes of power calculation, we have not assumed a full repeated measures analysis, but have instead analyzed change from baseline at a single time point. Second, we note that in trials such as this, the power of a non-parametric analysis is never much lower than its parametric analog (the "asymptotic relative efficiency" of the Wilcoxon test is at least 0.95), leading us to conclude that our parametrically based power calculations should apply with equal force to a non-parametric analysis.

Statistical analyses - Results from a sample of this size may not be normally distributed. Therefore, non-parametric statistical measures may be used. Primary outcome measures evaluating for change in KOOS and IKDC will be assessed at multiple points and will be analyzed for change between groups using Friedman two-way ANOVA for repeated measures. Synovial fluid analyses comparing the three groups at three time points will be analyzed using the Wilcoxon Signed Rank Sum Test with Hochberg corrections for multiple time points. Alternatively, if results are normally distributed or can be transformed (e.g., by log transformation) to meet the criteria for normality for parametric analysis, then repeated measures ANOVA will be utilized comparing treatment groups. P-values of less than or equal to 0.05 will be considered statistically significant. For those subjects enrolled in the extended follow-up sub-study the 24 month time point will be examined as an additional time point. Additionally, correlation analyses will be used to examine the relationship between biomarkers collected at Visits 1-3 and KOOS and IKDC values and MRI findings at 24 month follow-up.

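### KOOS and IKDC are both primary, with no deciding score or effect and no correction across scores; under assumed correlations the false-positive risk is about 7-10% (two outcomes) or 11-26% (six scores), not 5%

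*Combined protocol and SAP*

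**What the plan says.** The relevant text is the Statistical analyses paragraph, which is the same in all three copies of the protocol in the combined document.

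- **Primary outcomes:** "Primary outcome measures evaluating for change in KOOS and IKDC will be assessed at multiple points".
- **Primary test:** these "will be analyzed for change between groups using Friedman two-way ANOVA for repeated measures". If the data are normal or can be transformed to normality, then "repeated measures ANOVA will be utilized comparing treatment groups".
- **Threshold:** "P-values of less than or equal to 0.05 will be considered statistically significant".
- **Correction:** the synovial fluid analyses are tested "with Hochberg corrections for multiple time points". No other correction is stated.

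Objective 1 is written as a test and lists both instruments together: "Test the efficacy of Triamcinolone to alleviate knee pain (KOOS, IKDC) and improve patient-reported outcomes (PRO) following ACL rupture". The section on assessment by KOOS says: "The KOOS consists of 5 subscales (pain, other symptoms, function in daily living, function in sport and recreation, and knee-related quality of life". It describes no total score. Objective 2 lists seven synovial markers: IL-1α, IL-1β, NTX-I, CTX-II, and then "cartilage oligomeric protein (COMP) and glycosaminoglycan (GAG) and Xanthine Oxidase". The assay section also describes measuring IL-1Ra.

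Other parts of the protocol do not settle which result decides. The KOOS section calls sport/recreation and quality of life the most sensitive subscales. The power section uses KOOS pain and ADL. The early termination section says the study is powered on the blood and synovial fluid markers.

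**The concern.** A threshold of 0.05 per test gives a 5% false-positive risk only if one test decides. Here at least two outcomes are primary, and possibly six scores. The plan does not say whether the group effect or the group-by-time effect counts, and it gives no order of testing. Someone following the plan exactly could call the trial positive on any one of these results and choose which to report after seeing them.

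The authors did treat multiplicity as an issue, since they corrected the synovial fluid time points. They did not carry the correction to their primary outcomes or across markers. A falsely positive score would matter here because the trial is meant to inform a larger one.

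**Working it through.** **Inputs from the documents.** Four arms of 17; threshold 0.05 (two-sided assumed, as sidedness is not stated); two instruments; five KOOS subscales; pilot effect sizes 0.62 (KOOS pain) and 1.08 (KOOS ADL).

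**Assumed.** Correlation between scores, 0 to 0.9. Each score gets one valid between-group test with four arms, as repeated measures ANOVA would give. Friedman is a within-subject test, so the figures do not describe it; that is a separate problem.

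**Step 1: independent scores.** The chance of at least one p ≤ 0.05 among k true null tests is 1 − 0.95^k.
- k = 2: 1 − 0.95² = 0.0975.
- k = 6: 1 − 0.95⁶ = 0.265.

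**Step 2: correlated scores.** Simulated four-arm F tests, 17 per arm, no drug effect, 40,000 trials:

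| Correlation | Two outcomes, any p ≤ 0.05 | Six scores, any p ≤ 0.05 | Six scores, Hochberg |
|---|---|---|---|
| 0 | 0.096 | 0.264 | 0.051 |
| 0.3 | 0.097 | 0.247 | 0.049 |
| 0.5 | 0.089 | 0.214 | 0.043 |
| 0.7 | 0.086 | 0.174 | 0.036 |
| 0.8 | 0.080 | 0.148 | 0.031 |
| 0.9 | 0.072 | 0.114 | 0.024 |

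The simulation error near 0.05 is √(0.05 × 0.95 / 40,000) ≈ 0.001. A separate exact integral for equicorrelated two-sided z tests agrees: 0.070-0.098 for two and 0.108-0.265 for six. At correlation 0.95 it still gives 0.065 and 0.089.

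**Step 3: the unnamed model effect.** If either the group or the group-by-time effect may decide, one score alone has a simulated risk of 0.095-0.102 (5-7 visits, within-subject correlation 0.3 or 0.8). This is close to the 0.0975 for two independent tests.

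**Step 4: biomarkers.** Hochberg over time points holds each marker's family at or below about 5%. Across seven markers the ceiling, if they were independent, is 1 − 0.95⁷ = 0.302. Correlation would lower it. This assumes a valid between-group test; the signed-rank test named in the plan is a paired test.

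**Step 5: the plan's own power figures, then the cost of correcting.** The plan states 80% power for KOOS pain and more than 99% for KOOS ADL at 17 per group. For one change score, 17 v 17, two-sided t test, the noncentrality is d√(17/2) on 32 df: 0.62 × 2.915 = 1.81 and 1.08 × 2.915 = 3.15.

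| Score | Stated | Power at 0.05 | Power at 0.05/6 = 0.0083 |
|---|---|---|---|
| KOOS pain (0.62) | 80% | 42% | 18% |
| KOOS ADL (1.08) | >99% | 86% | 63% |

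The stated values do not reproduce for a two-group comparison. They come close only with a one-sample, one-sided formula (78.8% and 99.5%). That is a separate matter, and the false-positive figures do not depend on it. The cost of correction should be read from the recomputed columns.

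**The case against.** **The trial is preliminary.** The background section says it will supply data for a larger trial, and strict error control matters less in that setting. This stands and limits the severity. But objective 1 is framed as a test with a threshold, so the plan invites the reading that needs protecting.

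**The percentages rest on things the plan does not state.** This also stands. The correlations are assumed, and the six-score count is inferred from the KOOS description. The figures belong to the ANOVA alternative rather than the first-listed Friedman test. What survives is that the risk exceeds 5% on both counts throughout the range shown.

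**Stronger readings the documents do not support.**
- A reader might infer that no p-value is corrected. The synovial fluid tests are, over time points.
- A reader might take 26% as the trial's error rate. It is the independent-score end of the inferred six-score case.
- A reader might add separate tests of each active arm against placebo, which would raise the risk to 17-24% (two outcomes) or 26-56% (six scores). The plan neither states nor excludes such tests.
- A reader might conclude that KOOS pain has to be the primary score. The power section uses ADL as well, and the KOOS section favours other subscales, so that is a preference.

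**The power cost is for the wrong test.** This is partly right. The figures above are for a single change score, not a repeated-measures effect. In simulations with one effective arm at 0.62, an effect constant after baseline, Visit 1 kept as an outcome visit and compound symmetry, power for the group effect fell from 79-83% to 16% as the within-subject correlation rose from 0.3 to 0.8. Group-by-time power was 33-37%. No single figure can be given until the effect is named.

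**Conclusion.** The concern holds in a bounded form. The plan makes KOOS and IKDC primary, names no deciding score or effect, and applies 0.05 with no correction across them. If there is no drug effect, each score gets one valid four-arm test and the correlations lie between 0.9 and 0, the chance of at least one false-positive primary score is about 7-10% for two outcomes. It is about 11-26% if the five subscales and IKDC are tested separately. Hochberg over six brings it to about 2.5-5%. The existing Hochberg step also leaves the biomarkers uncorrected across markers. This should be corrected, but the trial's preliminary role means it does not by itself undermine the design.

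**What to change.** Change the SAP wording; no new data, visits or patients are needed.

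1. **Effect.** State one deciding between-group effect on change from the pre-treatment Visit 1.
2. **Scores.** List the KOOS and IKDC scores tested as primary and apply Hochberg across all of them. Naming one score from the power section as the single primary, with the rest secondary, is an acceptable alternative. The choice is the sponsor's.
3. **Arms.** Objective 1 compares triamcinolone with saline, and a significant four-arm test need not mean that any arm differs from placebo. A claim for a given arm therefore needs its active-v-placebo contrast, with Hochberg over the three arms, on a single named primary score. Run the contrasts in place of the four-arm test or only after it passes. Otherwise report contrasts with 95% confidence intervals and no significance claim.
4. **Biomarkers.** Apply one Hochberg across all assayed synovial markers (including IL-1Ra if it is tested) and the post-injection time points, with the pre-injection sample as baseline. Reconcile the reference to three groups with the four randomised.

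**Cost.** Fewer results can be called significant. For a single change score at 17 v 17, the strictest Hochberg step over six takes power from 42% to 18% for KOOS pain and from 86% to 63% for KOOS ADL; the later steps are less strict. A single named primary score avoids that loss. Arm claims cost more: with one effective arm at 0.62, simulated power to detect that arm is about 27%, or 24% if the four-arm test must pass first.

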2. Determine if intra-articular Triamcinolone therapy improves levels of a panel of inflammatory (cytokine), meniscus and cartilage metabolism and oxidative stress biomarkers as measured in synovial fluid from patients at relatively short-term time points after ACL injury (1-7 days, 10-17 days after injury and at time of surgery). Biomarkers to be tested include IL-1 α , IL-1 β , Collagen type I (NtxI) and collagen type II (CTXII) breakdown products, cartilage oligomeric protein (COMP) and glycosaminoglycan (GAG) and Xanthine Oxidase. Additionally, the change in IL-1 α and IL-1 β levels in the Triamcinolone treated and placebo individuals will be evaluated specifically for association with pain and function outcomes.

RESEARCH OBJECTIVES OF EXTENDED FOLLOW-UP SUB-STUDY:

1. Test the efficacy of a treatment protocol using triamcinolone acetate and knee arthrocentesis to improve patient-reported outcomes (PRO) following ACL rupture in a randomized, placebo controlled, double blinded, clinical trial at 24 months. All knees have undergone arthrocentesis and have received either the study drug or placebo within 1 week of ACL injury. The aim is to evaluate patients at the 24 time point following ACL reconstruction using established validated instruments for ACL injuries and PTOA (KOOS, IKDC, MARX).
2. Determine if specific synovial fluid biomarker levels and their response to early intervention with triamcinolone acetonide (Kenalog) correlates with improved clinical outcomes as measured by the KOOS. Early clinical trial results demonstrate that the collagen break down product CTX-II, the chondroprotective cross-linking molecule TSG-6 and cartilage oligomeric protein COMP show synovial fluid patterns similar to established models of early Osteoarthritis in humans and mice in patients treated with placebo. These patterns reverse in patients who received Kenalog at one or two time points prior to surgery. The goal of this aim is to identify if these biomarker levels may be predictive of better or worse outcome as measured by the KOOS at 24 months.
3. Determine if joint health as evaluated by MRI at 24 months following ACL injury is influenced by the initial treatment with Kenalog. Two years following ACL injury MRI analysis using standardized T2-mapping will be performed on 10 control subjects and 10 subjects who have received Kenalog injections.

INVESTIGATIONAL PLAN

Description of Overall Study Design and Plan (See Figure 1 for study timeline)

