This study is a multicenter, randomized, placebo controlled, double blinded, clinical trial. This trial will enroll 68 subjects between the ages of 14 and 33. This trial will be conducted at two clinical centers, the University of Kentucky and Vanderbilt University, as well as established criteria and support of the Multicenter Orthopaedic Outcome Network (MOON). A sub-study involving extended follow-up of patients, 24 months post-surgery will occur at the University of Kentucky clinical center only. This sub-study will involve 20 subjects of the initial University of Kentucky cohort returning for one additional follow-up time point.

Description of observations and measurements to be made in this study:

Assessment of Pain and Function by KOOS – This trial will use the standardized patient self-report Knee Injury and Osteoarthritis Outcome Score (KOOS) instrument to assess pain and function in response to the intervention for acute ACL injury. The KOOS consists of 5 subscales (pain, other symptoms, function in daily living, function in sport and recreation, and knee-related quality of life). The 5 separate subscales provide a complete picture of subjects' perceptions of

their knee injury and consequences to their daily activities, etc.. KOOS includes the WOMAC osteoarthritis index, which allows for potential comparison with other earlier studies. The KOOS has high test-retest reproducibility (ICC > 0.75). The KOOS subscales for function in sport and recreation and knee-related quality of life have been shown to be the most sensitive subscales pre-operatively and change the most post-operatively (44). This trial will supplement the KOOS with function score assessments from the International Knee Documentation Committee (IKDC) form for evaluation of knee ligament injuries [45]. In addition to the KOOS and IKDC, those completing the extended follow-up sub-study will also complete the MARX activity scale as an assessment of current physical activity level at the 24 month follow-up.

Specific Pain assessments - Pain coping strategies are important in understanding improvements in pain and psychological disability [46-48]. This trial will use a simple Likert pain scale, the Coping Strategies Questionnaire (CSQ) and ‘pain

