- Patient reported outcomes (PROs) administered

Visit 3 (day of surgery)

- Lab tests(urine and 10cc of blood)
- Pain Questionnaires administered prior to surgery
- Knee aspiration (in the operating room under anesthesia)
- Patient reported outcomes (PROs) administered prior to surgery

Visit 4 (1-2 weeks post surgery)

- Pain Questionnaires administered
- Knee aspiration (if clinically indicated)
- Patient reported outcomes (PROs) administered

Visit 5 (4-6 weeks post surgery)

- Patient reported outcomes (PROs) administered
- Pain Questionnaires administered

Visit 6 (6 months follow-up/Early Termination Visit)

- Patient reported outcomes (PROs) administered
- Pain Questionnaires administered

Optional Extended Follow-Up Sub-Study (To Include 20 University Of Kentucky Subjects)

Visit 7 (24 (+/- 3) month follow-up)

- Patient reported outcomes (PROs) administered
- Pain Questionnaires administered
- Research Specific MRI

ADVERSE EVENTS

Any significant change in a subject's health from screening will be recorded and reported as adverse events while the subject is taking part in the study. Adverse Events (AEs) will include but are not limited to severe post-administration pain requiring treatment, infection of the injection site or the knee joint, ER visit following the administration of the study drug at visit 1 or 2. Due to the short half life of the drug we do not expect any SAE's related to the drug administration later than after the date of ACL surgery. During the observation time (time of surgery to 6 months post-op) other, non-drug related, SAEs may occur which will be recorded and reported.

Any reported SAE occurring during the study must be reported by the sponsor to the Food and Drug Administration and the appropriate Institutional Review Board. Any SAE due to any cause, whether or not related to the study drug, must be reported within 24 hours of when the Investigator becomes aware of the event. Investigators who need to report SAEs to the sponsor may do so by utilizing FDA Form 3500A the sponsor provided SAE reporting form and faxing report to [contact].

Plan for unexpected adverse event (AE) reporting. Serious AEs will be reported to Human Subjects/IRB within 48 hr. Unanticipated events will be reported to the IRB.

Monitoring of adverse events. Adverse events will be monitored via exams, vital signs, review of subject's medical chart, and documented. Each visit will be documented with a progress note in the research chart.

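### In the third protocol text, 24-month KOOS and IKDC are main-study mailed outcomes, but the 24-month analysis sentence still names only MRI sub-study enrollees

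*Combined protocol and SAP*

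**What the plan says.** The combined protocol and SAP contains three full protocol texts. The title blocks before the second and third both read Version 7, 4 May 2015, although their contents differ. The point lies inside the third text.

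- **Research Objectives of the Current Study, objective 1** (KOOS, IKDC and other patient-reported outcomes): the list of assessment times now ends "post-op, and 24 months post-op) following ACL reconstruction".
- **Research Objectives of Extended Follow-up Sub-study**: one objective remains, MRI at 24 months in 10 control and 10 Kenalog subjects.
- **Duration of Patient Enrollment**: Kentucky subjects are followed for 24 months, and 20 subjects are recruited to the MRI sub-study.
- **Visit list**: Visit 7 (24 months, by mail) collects patient-reported outcomes and pain questionnaires and carries no sub-study label. Visit 8 is the optional 20-subject sub-study and lists only the MRI.
- **Assessment of Pain and Function by KOOS**: "current physical activity level at the 24 month follow-up study will be evaluated using the MARX activity scale", with no tie to the sub-study.
- **Statistical analyses**: change in KOOS and IKDC "will be assessed at multiple points" and is "analyzed for change between groups using Friedman two-way ANOVA for repeated measures". On 24 months the section then says: "For those subjects enrolled in the extended follow-up sub-study the 24 month time point will be examined as an additional time point".

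**The concern.** The last sentence is the only one in the statistical section that names a population for the 24-month time point, and it names the sub-study enrollees. In this text those are the roughly 20 people who accept an optional MRI, not the people who are mailed the questionnaires.

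If an analyst follows it for KOOS and IKDC, the arms are compared in a set formed after randomisation. Entry is voluntary, with its own consent addendum, and the Exclusion Criteria remove anyone injured or re-injured in either knee after reconstruction. A 24-month difference could then partly reflect who was kept. Mailed scores from the other followed subjects would go unused for an objective that the main study states. Because the sentence can be read in more than one way, two analysts could also defend different populations after seeing the data.

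**Working it through.** The plan gives no sample size or power for 24 months, so there is no stated figure to reproduce. The check is a comparison of the texts, followed by the size of the consequence.

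**Step 1. Where the sentence came from.**

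| Element | Second text | Third text |
|---|---|---|
| 24-month patient-reported outcomes as an objective | Sub-study objective 1: "to improve patient-reported outcomes (PRO) following ACL rupture in a randomized, placebo controlled, double blinded, clinical trial at 24 months" | Main-study objective 1; no longer a sub-study objective |
| 24-month questionnaire visit | Visit 7, under "Optional Extended Follow-Up Sub-Study (To Include 20 University Of Kentucky Subjects" | Visit 7 by mail, outside the sub-study |
| MARX at 24 months | "those completing the extended follow-up sub-study will also complete the MARX activity scale" | Not tied to the sub-study |
| Followed to 24 months | The 20 sub-study subjects | Kentucky subjects; 20 subjects for MRI |
| 24-month analysis sentence | Names sub-study enrollees | Same sentence, word for word |

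The sentence fitted the second text, where the only 24-month visit belonged to the sub-study. In the third text the design around it changed and the sentence did not. Objective 1 shows the same partial editing: it still announces five time points but now lists six.

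The flow chart in Appendix A of the third text is not relied on. As extracted, its repeated questionnaire rows are blank at Visit 6, where the visit list requires them, so the columns may have shifted. KOOS and IKDC are marked at Visit 7 either way.

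**Step 2. Scores left out on the natural reading.** Inputs from the documents: 20 sub-study subjects, 10 control and 10 Kenalog; four groups of 17, so control to Kenalog is 1:3; 68 subjects over two centres. Kentucky enrolment N is not given and is below 68, because Vanderbilt also enrols. Assumption: N = 40 to 51, with the 1:3 ratio holding at Kentucky. A smaller N fits poorly: N = 34 gives 34/4 = 8.5 expected controls, fewer than the 10 planned for MRI. Even N = 40 gives exactly 10, so every expected control would have to join.

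- Full mail return, share left out = 1 − 20/N. N = 40: 20/40 = 50%. N = 51: 31/51 = 61%.
- 80% return (assumption), all 20 sub-study subjects replying, share left out = 1 − 20/(0.8N). N = 40: 12/32 = 37.5%, about 38%. N = 51: 20.8/40.8 = 51%.

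**Step 3. Precision.** Standard error of pooled Kenalog versus control, in SD units, = √(1/n₁ + 1/n₂). The statistical section does not name this contrast for KOOS; it serves only as a yardstick.

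| Set | Control v Kenalog | SE |
|---|---|---|
| Sub-study only | 10 v 10 | 0.45 |
| N = 40, full return | 10 v 30 | 0.37 |
| N = 51, full return | 12.75 v 38.25 | 0.32 |
| N = 40, 80% return | 10 v 22 | 0.38 |
| N = 51, 80% return | 10.2 v 30.6 | 0.36 |

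The 10 v 22 split keeps Step 3 consistent with Step 2: if all 20 sub-study subjects reply, all 10 controls are among the 32 replies.

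**The case against.** The strongest reply is that the text does not compel the restriction. The sentence does not say that other subjects are excluded, and it names no outcome. In the third text the sub-study's extra 24-month observation is an MRI, so the sentence may mean the MRI. The general rule on KOOS and IKDC at several time points could cover every mailed score. The following sentence, on correlations, uses 24-month KOOS and IKDC without mentioning the sub-study. These points stand: a reader might infer that the plan definitely discards the other mailed scores, and the documents do not support that. What remains is that the only population named for 24 months is the sub-study.

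Second, it is not known whether the third text governs. In the first and second texts the sentence fits the design. The third text is also only partly converted: follow-up for all subjects is still six months, and the adverse-event section still ends the observation time at 6 months. This stands, and it is why the sponsor must say which text applies.

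Third, the wider set is not the full randomised set either. It depends on mail return, on site, and on the rule under Early Termination of Subjects from Study that drops from the efficacy analysis, and replaces, those who discontinue before Visit 5. This stands too. The change reduces selection but does not remove it.

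Finally, the sizes rest on an assumed N and return rate. They show scale and are not estimates.

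**Conclusion.** The third text is inconsistent about who enters the 24-month KOOS and IKDC comparison. On the natural reading of its analysis sentence, that comparison would use about 20 opt-in subjects selected on no re-injury after reconstruction. If Kentucky enrols 40 to 51 (assumption), 50% to 61% of 24-month scores would be left out at full mail return, or 38% to 51% at 80% return with all sub-study subjects replying.

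Selection is the main issue. The precision gain is modest: a standard error of 0.45 falls to between 0.32 and 0.38 SD units over the cases shown. A reader might infer that the result would be biased towards or against Kenalog, or that the 10:10 split is itself a bias. The documents support neither: they give no basis for a direction, and unequal sampling of arms does not by itself bias a between-arm comparison. No error is claimed in the flow chart or in the correlation sentence.

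The correction is worth making but lower priority, since it concerns a later time point outside the power calculation.

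**What to change.** Replace the sentence in Statistical analyses with:

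> The 24-month KOOS and IKDC (Visit 7) will be compared between randomised groups in all subjects followed to 24 months who are in the efficacy analysis, whether or not they enrol in the MRI sub-study, as a separate change-from-baseline analysis; MRI analyses are limited to sub-study subjects.

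The sub-study's re-injury exclusion should not carry over to Visit 7. The 24-month analysis is kept separate because the Friedman test needs complete rows, and under Duration of Patient Enrollment only Kentucky subjects are followed to 24 months.

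Two clarifications go with it:

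- Reconcile objective 1 and the visit list, which set no site limit at 24 months, with Duration of Patient Enrollment, which limits it to Kentucky, so that the population is named.
- State which protocol text governs.

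The cost is one sentence and these two clarifications. No new data are collected. The downside is slightly more analysis work, with a 24-month result that depends on mail return.
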